# 2.2. How results of this project will be used (e.g., Presentation? Publication? Thesis? Dissertation?)

It is currently expected that this work will form the base of [name] dissertation. The results from this project will be submitted for publication and an abstract will be submitted for acceptance to a professional conference; however, no specific patient information will be disclosed.

### 3. Participants

#### 3.1. Inclusion and exclusion criteria

a) Inclusion Criteria:

Auburn University employees or an adult sponsored dependent of an active employee who was insured by the Auburn University Health and Pharmacy Insurance Plan during 2015 and/or 2016 and who are enrolled in the Auburn University Health Plan for the 2017 plan year, who meet the following criteria:

- Have completed their "Healthy Tigers" screening for the 2015, 2016, or 2017 plan year (completed by the "Healthy Tigers" staff or through submission of a "Healthy Tigers" healthcare provider form OR is a patient of the AU Employee Pharmacy and is enrolled in the TigerMeds program OR is a participant in the Pharmacy Practice Experience (PPE) who is seen within the AUPCC AND has a BMI (kg/m2) screening value >24.9 AND has two or more of the following CVD risk factors:
  - a) screening values classified in the "yellow" or "red" zone for:
    - Systolic blood pressure (mmHg): Yellow zone:  $\ge$ 140, Red zone:  $\ge$ 160;
    - Diastolic Blood pressure (mmHg): Yellow zone: ≥90, Red zone: ≥ 100;
    - Fasting blood glucose (mm/dL): Yellow zone:  $\geq$ 100, Red zone:  $\geq$ 126
    - Blood glucose(random) (mg/dL): Yellow zone: 140-200, Red zone > 200
    - Total Cholesterol (mg/dL): Yellow zone:  $\geq$ 200, red zone:  $\geq$ 250
  - b) Have a pre-existing diagnosis of hypertension, pre-diabetes, or hypercholesterolemia
  - c) Current smoker ( $\geq 1$  cigarette/day)
  - d) Are: male (age: 55-80) or female (age: 60-80)
  - e) A family history of premature coronary heart disease
  - f) High risk ethnicity: Black, African American, American Indians/Alaska Natives, Non-Hispanic blacks, Mexican-Americans, Asian, Hispanic/Latino

- b) Exclusion Criteria:
  - 1. Minors that are less than 19 years of age
  - 2. Individuals who are not enrolled in the Auburn University health insurance program for the 2016 plan year at baseline and have not yet completed initial visit
  - Individuals who have not completed their 2015 "Healthy Tigers" biometric screening between January 1st and December 31st, 2015 (these can be completed by the "Healthy Tigers" staff or by submitting a healthcare provider form from the individuals' physician to the "Healthy Tigers" office), unless enrolled in TigerMeds.
  - 4. Individuals who are pregnant or who intend to become pregnant during the 12-week health and wellness challenge.
  - 5. Individuals who anticipate absence or travel throughout the study that would interfere with their ability to complete the analysis at the mid-point and end of challenge.
  - 6. Patients with a peanut, tree nut, or olive oil food allergy or intolerance.
  - 7. Patients who are unable or unwilling to travel to Auburn University main campus for live health and wellness challenge events, individual assessments, personal appointments, and pre- and post- data collection
  - 8. Individuals who have NOT been stabilized on medication to treat or manage high blood pressure, high cholesterol, dyslpidiemia, or pre-diabetes for at least 12 weeks prior to the study.
  - 9. Patients who do not have access to the internet and therefore unable to complete the education portion of the study
  - 10. Individuals who have a pacemaker
  - 11. Patients who decline participation during informed consent

# **3.2. Recruitment methods**

- 1. Recruitment will be expanded to include participants enrolled in the Pharmacy Practice Experience who are seen within the AUPCC
- 2. Recruitment will take place from November 2016-February 2017 until the project is filled
- 3. A letter describing the research study including the name of the project, the investigators, the inclusion and exclusion criteria, study description, will be e-mailed to all 2015, 2016, and 2017 "Healthy Tigers" and "TigerMeds" participants.
- 4. Patients that are screened in the "Healthy Tigers" program OR patients who are a part of the PPE program and seen within the AUPCC during the months of November 2016- February 2017 (until the study is filled) and meet criteria on the "Healthy Hearts Program Eligibility Screener" will receive a promotional flier (see Appendix A) during their screening process. If the patients have questions about the study, they will be directed to [name] or a member of the "Healthy Tigers" staff.
- 5. Messages about the Healthy Hearts Program will be sent to AU employees via the AU Daily

- 6. Participants of ScaleBack Alabama who weigh in at the AUPCC during the months of January-February 2017 will receive a promotional flyer
- 7. Social media announcements on Facebook, Twitter, and Instagram.

### 4. Project Design and Methods

# 4.1. Methods for consenting participants

Participants will be seen at the Auburn University Pharmaceutical Care Clinic (AUPCC) for their initial "Healthy Tigers" Healthy Hearts Program consenting visit. During this visit, individuals will be screened for eligibility. Once eligibility is determined, a printed copy of the Informed Consent will be given to and discussed with the eligible individual. If the participant chooses to participate, their signature will be obtained on the consent form. Participants will make an appointment for their Baseline visit.

### 4.2. Research design and methods

- Participants will be seen at the Auburn University Pharmaceutical Care Clinic (AUPCC) for their initial "Healthy Tigers" Healthy Hearts Program consenting visit. The assessment will include a health and wellness interview, International Physical Activity Questionnaire, Diet History Questionnaire II, a Mediterranean diet knowledge/adherence survey, and the completion of the eligibility form. During this visit, the letter of consent will be given to and discussed with the participant. If the participant chooses to participate, their signature will be obtained on the consent form.
- 2) a) Participants will then return to the Auburn University Pharmaceutical Care Clinic (AUPCC) for their baseline "Healthy Tigers" Healthy Hearts Program visit. Pharmacists and pharmacy residents, employed by the AUPCC will obtain the following: height measurement (inches), weight measurement (pounds), Calculated BMI (kg/m2) measurement of body composition (using bioelectrical impedance analysis) (% body fat, pounds of fat, pounds of lean mass, pounds of total body water), waist measurement (inches), hip measurement (inches), Waist to Hip Ratio, Waist to Height Ratio, Systolic blood pressure (mmHg), Diastolic blood pressure (mmHg), resting pulse (bpm), fasting blood glucose (mg/dL), fasting total cholesterol (mg/dL), fasting LDL-cholesterol (mg/dL), fasting HDL-cholesterol (mg/dL), fasting Triglycerides (mg/dL), total Cholesterol to HDL ratio, Atherosclerotic cardiovascular disease risk (ASCVD) Score (%), fasting insulin mI/L, fasting leptin ng/mL, IL-6 (pg/mL), tumor necrosis factor-α (pg/mL), urinary tyrosol and hydroxytyrosol. These measurements will be repeated at week 6 and week 12 of the trial.
  - b) At this baseline appointment, the patient will also receive a baseline medication therapy management (MTM) assessment by a pharmacist in order to identify any potential or actual drug-related problem (DRPs), and to monitor for efficacy and safety of all medications, make recommendations for vitamins, minerals, and supplements, and provide preventative care recommendations (such as immunizations, osteoporosis screenings, colonoscopy, mammograms, and other recommended medical screenings that are recommended for the patient's age, gender, and concomitant disease states and medications).

- c) All subjective and objective medical information collected during this appointment will be recorded in the CompuGroup Medical (CGM) electronic medical record (EMR) that is used in the Auburn University Pharmaceutical Care Center (AUPCC) and the "Healthy Tigers" programs. This EMR is a secure medical record that meets all HIPAA requirements and has been reviewed by the Harrison School of Pharmacy (HSOP) HIPAA officer, the Auburn University HIPAA officer, and the AU HIPAA consultant, and meets all legal and security requirements. These data will be perpetually stored in this EMR as required of medical data. Access to this EMR is restricted to authorized personnel only.
- 3) Baseline, 6 week and 12 week Appointments
  - a) Participants will then return to the Auburn University Pharmaceutical Care Clinic (AUPCC) for their baseline "Healthy Tigers" Healthy Hearts Program visit. Pharmacists and pharmacy residents, employed by the AUPCC will obtain the following: height measurement (inches), weight measurement (pounds), Calculated BMI (kg/m2) measurement of body composition (using bioelectrical impedance analysis) (% body fat, pounds of fat, pounds of lean mass, pounds of total body water), waist measurement (inches), hip measurement (inches), Waist to Hip Ratio, Waist to Height Ratio, Systolic blood pressure (mmHg), Diastolic blood pressure (mmHg), resting pulse (bpm), fasting blood glucose (mg/dL), fasting total cholesterol (mg/dL), fasting LDL-cholesterol (mg/dL), fasting HDL-cholesterol (mg/dL), fasting Triglycerides (mg/dL), total Cholesterol to HDL ratio, Atherosclerotic cardiovascular disease risk (ASCVD) Score (%), fasting insulin mI/L, fasting leptin ng/mL, IL-6 (pg/mL), tumor necrosis factor-α (pg/mL), plasma α linolenic acid, urinary tyrosol and hydroxytyrosol. These measurements will be repeated at week 6 and week 12 of the trial.

#### All data will be collected at:

Auburn University Main Campus Auburn University Pharmaceutical Care Clinic (AUPCC) Harrison School of Pharmacy [name]

- b) At the baseline appointment, the patient will also receive a baseline medication therapy management (MTM) assessment by a pharmacist in order to identify any potential or actual drug-related problem (DRPs), and to monitor for efficacy and safety of all medications, make recommendations for vitamins, minerals, and supplements, and provide preventative care recommendations (such as immunizations, osteoporosis screenings, colonoscopy, mammograms, and other recommended medical screenings that are recommended for the patient's age, gender, and concomitant disease states and medications).
- c) All subjective and objective information collected during this appointment will be recorded in the CompuGroup Medical (CGM) electronic medical record (EMR) that is used in the Auburn University Pharmaceutical Care Center (AUPCC) and the "Healthy Tigers" programs. The EMR is a secure medical

record that meets all HIPAA requirements and has been reviewed by the Harrison School of Pharmacy (HSOP) HIPAA officer, the Auburn University HIPAA officer, and the AU HIPAA consultant, and meets all legal and security requirements. These data will be perpetually stored in this EMR as required of medical data. Access to this EMR is restricted to authorized personnel only. Participants will also have a paper research chart. No identifying data identifying information will be kept in the research chart. Participants will be assigned a personal, unique, and confidential study code at this visit. This study code will be placed at the top of all data sheets that are placed in the research chart. Identifying information will be stored electronically as part of the electronic medical records of the AUPCC for the individual patients. The code list linking the study code to the EMR will be stored in the medical records room the AUPCC (2155C) which has controlled access. The specific cabinet in which it will be stored has a key lock and the key is stored in a password-protected lockbox.

- d) At the end of the baseline and 6 week appointments, participants in The Mediterranean Diet (MD) group will receive 3L of olive oil and 3 pounds of mixed nuts. Participants in the MD group will be educated by oral and written means, on consumption goals. Participants will be asked to return any unused supplements at the midpoint (week 6) and 12-week appointment. Information will be provided to the participant on how to access nutritional information used within this study and how to access the educational programming. Written instructions will also be provided.
- e) Participants will complete 3 surveys/questionnaires at their baseline visit, 6 week, and 12 week appointments. The Mediterranean diet screener and the International Physical Activity questionnaire will be completed in person. Participants will complete the web-based version of the Diet History Questionnaire II.

Participant Task		Total Involvement Time
In-Person Visits to the AUPCC	Estimated Time	
Consenting visit	45 minutes	
Baseline visit	45 minutes	
6 week visit	45 minutes	
12 week visit	45 minutes	
Total In-Person Involvement		180 Minutes
Time		
Web-Based Tasks		
Diet History Questionnaire (x3)	30 minutes each	90 minutes
Nutrition Education Modules (x7)	10 minutes each	70 minutes
Total Web-Based Involvement		160 minutes

4) Participant Involvement Time

Time	

# **Total Participant Involvement Time**

#### 340 minutes

- 5) STUDY REQUIREMENTS
  - a) The participants will be asked to follow a dietary pattern that is associated with their assigned intervention group. The Mediterranean Diet (MD) group will be given supplements of extra virgin olive oil (EVOO) and mixed nuts. Participants in this group will be asked use these supplements as a part of their daily intake. A total of 6 L of EVOO and 6 pounds of mixed nuts (3 pounds raw walnuts and 3 pounds raw almonds) will be administered throughout the study. Participants in the MD group will be given 3 L of EVOO and 3 pounds of mixed nuts at the baseline appointment asked to return unused portions of at their 6-week appointment. At that time they will be given a new supplementation of 3 L or EVOO and 3 pounds of mixed nuts. Participants will be given the same instructions for use and asked to return unused portions at the end of the study (week 12).
  - b) The participants might have follow-up appointments scheduled with the pharmacist within the AUPCC depending on the patient's personal care plan that is developed at baseline. For instance, if a patient has potential or actual drug-related problems that are identified on their baseline MTM appointment, then the pharmacist will schedule follow-up appointments that are appropriate for the problem and the plan of care that is developed to address these problems. This will be done consistently between all patients in the study, regardless of the randomization (the pharmacist and the will be blinded concerning which group the patient is randomized to concerning dietary intervention).
  - c) Narrated nutrition education presentations will be developed by a registered dietitians, dietetic interns, graduate students, and faculty. These presentations will be loaded on the "Healthy Hearts Program" website. The participants will be asked one presentation weekly for the first 6 weeks of the study and then one additional education module at week 9. A post-presentation assessments will load after the presentation is completed, and completion of the assessment will be used as verification that the participant watched the presentation.
  - d) The participant will complete the following at baseline, week-6 and week 12 of the study: Diet History Questionnaire II, International Physical Activity Questionnaire, and a Mediterranean diet knowledge and adherence questionnaire.
  - e) For patients with a diagnosis of Hypertension or an elevated blood pressure reading during a "Healthy Tigers" screening that is in the yellow or red zone, home blood pressure monitoring might be integrated into the medication therapy management plan of care.

- f) For patients with a diagnosis of pre-diabetes, or who have an elevated blood glucose reading during a "Healthy Tigers" screening that is in the yellow or red zones, home blood glucose monitoring might be integrated into the medication therapy management plan of care.
- g) All participants will be asked to return to the AUPCC at weeks 6 and 12 for a repeat "Healthy Tigers" analysis and MTM consultation.

# 4.3. Measurement Procedures

# Questionnaires

- 1) A registered dietitian or trained nutrition student will administer the following:
  - a) International Physical Activity Questionnaire
  - b) Mediterranean Diet Knowledge and Adherence Questionnaire
- 2) Participants will be instructed on how to complete the following questionnaire from home computer
  - a) Food Frequency Questionnaire- Diet History Questionnaire II (DHQII)

# **Blood pressure (BP)**

- 1) Blood Pressure (4): Blood pressure will be taken with a mercury sphygmomanometer with the Korotkoff's sound technique
  - a) Patient will be seating comfortably, with back supported, legs uncrossed, and upper arm bare.
  - b) Patient's arm should be supported at approximately heart level
  - c) Cuff bladder should encircle 80% or more of the patient's arm circumference
  - d) Mercury column should be deflated at 2-3 mm per second
  - e) The first and last audible sounds should be recorded as systolic and diastolic pressure, respectively. Measurements should be given to the nearest 2 mm Hg.
  - f) Neither the participant nor the person taking the measurement should talk during the procedure

**Anthropometric measurements:** *Anthropometric measurement procedures taken from the National Health and Nutrition Survey (NHANES) Anthropometry Procedures Manual. (5)* 

- 1) Height: Participant's height will be measured via standing height.
  - a) Height will be measured using a wall-mounted calibrated stadiometer
  - b) Prior to measurement, participant will be asked to remove hair ornaments, jewelry, buns.
  - c) Participant is to stand up straight against the backboard with the body weight evenly distributed with both feet flat with heels together and toes apart
    - i) Depending on the overall body configuration of the participant, the following four points must make contact with the stadiometer backboard-head, shoulders, buttocks, and heels, examples of possible exceptions:
      - 1. Some overweight individuals cannot stand straight while all four points touch the backboard

- 2. Participants with kyphosis a forward curvature of the spine that appears as a hump at the upper back may make contact not possible
- d) Align the head in the Frankfort horizontal plane (See Figure 1)
  - i) In the Frankfort horizontal plane the horizontal line from the ear canal to the lower border of the orbit of the eye is parallel to the floor and perpendicular to the vertical backboard
- e) Lower the stadiometer head piece so that it rests firmly on the top of the participant's head
- f) Instruct participant to stand as tall as possible and take a deep breath, and hold this position.
- g) Record result in inches.
- 2) Weight: Participants will be weighed on a calibrated scale at the AUPCC
  - a) Ask participants to remove shoes, purses/bags, jackets or bulky outerwear prior to stepping on the scale
  - b) Record weight in pounds provide weight to patient.
- 3) Waist Circumference:
  - a) Ask participant to remove any jackets or bulky outerwear. If participant feels comfortable, ask to gather his/her shirt above the waist.
  - b) Ask participant to place hands on opposite shoulders.
  - c) Stand on participant's right side. Palpate the hip area to locate the right ilium of the pelvis. With a cosmetic pencil draw a horizontal line just above the uppermost lateral border of the right ilium. Cross this mark at the midaxillary line, which extends down from the armpit down the side of the torso.
  - d) Extend the measuring tape around the waist. Position the tape in a horizontal plane at the level of the measurement mark. Check that the tape is parallel to the floor and lies snug but does not compress the skin.
  - e) Always position the zero end of the tape below the section containing the measurement value.
  - f) Take and record the measurement to the nearest 0.1 cm.

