# **Venipuncture blood draw-** *Phlebotomy procedures will follow the World Health Organization's Guidelines on drawing blood: Best practices (6)*

- 1) **Overview**: Participant will be instructed not to eat or drink anything, other than water, after midnight the day of their baseline, 6-week, and 12-week visits. Phlebotomy of a peripheral arm vein will be performed by AUPCC clinicians (pharmacists and pharmacy residents) who have been phlebotomy trained, using sterile procedures and seated position. A sterile bandage will cover the phlebotomy site after the procedure and arm will be elevated to ensure that bleeding has stopped. The participant will be observed for any lightheadedness, bruising or bleeding during and after the procedure.
  - a) If the participant is lightheaded, he/she will be reclined until symptoms resolve

- b) If the participant is asymptomatic after the phlebotomy procedure, he/she will be released
- c) A maximum of 3 attempts to access a vein will be allowed at each visit, for each participant. If 3 unsuccessful attempts to access a vein are made, the participant will be excused from this portion of the study.

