# 4) **Procedure**

- a) Identify participant.
- b) Select the site (preferably at the bend of the elbow). Palpate the area; locate a vein of good size that is visible, straight, and clear. The vein should be visible without applying the tourniquet.
- c) Apply a tourniquet, 4-5 finger widths above the selected site.
- d) Ask the patient to forma fist so that the veins are more prominent
- e) Put on well-fitting, gloves.
- f) Disinfect the site using 70% isopropyl alcohol and allow to dry. DO NOT touch the site once disinfected.
- g) Anchor the vein by hold the patient's arm and placing a thumb BELOW the venipuncture site. **DO NOT touch the cleaned site; in particular, DO NOT place a finger over the vein to guide the needle.**
- h) Perform venipuncture. Enter the vein swiftly at a 30 degree angle.
- i) Once sufficient blood has been collected, release the tourniquet BEFORE withdrawing the needle
- j) Withdraw the needle gently and give the patient a clean gauze or dry cottonwool ball to press gently on the site. Ask the patient NOT to bend the arm.
- k) Discard the used needle and syringe or blood sampling device immediately into the sharps container
- 1) Check the label and forms on vacuum tube for accuracy

- m) Place items that can drip blood or body fluids into the "Biohazardous" waste container
- n) Remove gloves and place them in the general waste.
- o) Perform hand hygiene

**Urine collection** *A clean catch urine sample will be obtained from the participant. Procedures are derived from the U.S. National Library of Medicine. (7)* 

- 1) Participant will be instructed not to void immediately prior to baseline, 6-week, and 12- week appointments.
- 2) Participants will be given verbal and written instructions on how to provide a clean catch urine sample. Instructions will include:
  - a) You will use a special kit to collect the urine, it will include a cup and two wipes.
  - b) Wash your hand with soap and warm water
  - c) Females
    - i) Sit on the toilet with legs spread apart. Use two fingers to spread open the labia.
    - ii) Use a wipe to clean the inner folds of the labia. Wipe front to back.
    - iii) Use a second wipe to clean over the opening where urine comes out (urethra), just above the opening of the vagina.
    - iv) Keeping your labia open, urinate a small amount into the toilet bowl, then stop the flow of urine
    - v) Hold the urine cup a few inches from the urethra and urinate until the cup is about half full.

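### Shirt state at the waist measurement, and the order of urine collection and weighing, are not fixed across visits, so change in waist, weight and body composition can include clothing and urine

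*Combined protocol and SAP*

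**What the plan says.** Section 4.3 (Measurement Procedures, Anthropometric measurements) covers waist and weight.

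- **Waist.** Outerwear comes off, and then: "If participant feels comfortable, ask to gather his/her shirt above the waist". Later steps of the same procedure draw a pencil mark above the hip bone and position the tape there: "Check that the tape is parallel to the floor and lies snug but does not compress the skin". The result is read finely: "Take and record the measurement to the nearest 0.1 cm".
- **Weight.** The preparation is: "Ask participants to remove shoes, purses/bags, jackets or bulky outerwear prior to stepping on the scale". Remaining clothing and voiding are not mentioned.
- **Urine.** The urine collection part of 4.3 says: "Participant will be instructed not to void immediately prior to baseline, 6-week, and 12- week appointments".
- **Fasting.** The blood draw part of 4.3 says: "Participant will be instructed not to eat or drink anything, other than water, after midnight". Water intake before the visit is therefore not limited.
- **Bioimpedance.** Sections 4.2 and 4.5 list percent fat, fat mass, lean mass and total body water as measured and compared over time. Section 4.3 gives no procedure for them.

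Section 2.1 names body mass index and waist circumference as secondary outcomes and blood lipids as primary. Aim 1 asks whether participants improve by week 12; Aim 2 compares the diets. Section 4.5 compares baseline with weeks 6 and 12 by Student's t test. On timing, section 3.2 says: "Recruitment will take place from November 2016-February 2017".

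**The concern.** A change score is only as clean as the match between the two measurements behind it. Here two conditions can differ between visits without anyone knowing.

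First, a participant may keep the shirt down at baseline and lift it at week 12, or the reverse. The waist procedure is also not consistent with itself: the pencil mark and the reference to skin presume a bare waist, while the comfort clause allows something else.

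Second, the participant may be weighed and put through bioimpedance before the urine sample at one visit and after it at another, since no order is stated.

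For Aim 2 the result is extra variance. For Aim 1 there is no comparator to cancel a common drift. Baselines would fall mostly in winter, with week 12 visits roughly from February to May. Lighter clothing, or greater ease with the procedure at a later visit, would lower waist or weight without any dietary effect. Both trends are inferences; the documents report neither. If the skin-or-shirt state is not recorded, the analyst cannot test for such a drift or adjust for it.

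**Working it through.** The plan states no sample size, SD, effect size or alpha, so there is no figure of its own to reproduce. Everything below is illustration. **Assumed inputs:** cloth thickness, share of participants switching, SD of change, number of participants, bladder difference and height. The only figure taken from the plan is the 0.1 cm reading unit for waist.

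**1. Effect of a cloth layer.** A layer of thickness t adds 2πt to a circumference.
- t = 1 mm: 2π × 0.1 cm = 0.63 cm
- t = 2 mm: 2π × 0.2 cm = 1.26 cm

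That is about 6 to 13 times the reading unit.

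**2. Mean shift if switching goes one way.** Shift = share moving from shirt to skin × layer effect.
- 20% × 0.63 = 0.13 cm
- 20% × 1.26 = 0.25 cm, and 40% × 0.63 = 0.25 cm
- 40% × 1.26 = 0.50 cm

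**3. Effect on a pre-post test (Aim 1).** Section 4.5 does not say whether the t test is paired; a paired two-sided 5% test is assumed, with n = 40, SD of change 4 cm and no true change. The critical value on 39 degrees of freedom is 2.023, and the noncentrality is shift / (4/√40).

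| Mean shift (cm) | Noncentrality | Rejection rate |
|---|---|---|
| 0.126 | 0.20 | 5.4% |
| 0.25 | 0.40 | 6.7% |
| 0.50 | 0.79 | 12.0% |

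With an SD of change of 3 cm, the same three shifts give 5.8%, 8.1% and 17.7%.

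**4. Effect on the between-arm comparison (Aim 2).** Suppose a fraction p of participants differ in shirt state between visits, equally often in each direction and equally in both arms. The variance of change becomes s² + p·d², where d is the layer effect and s the SD of true change. The required sample size grows by the factor 1 + p·d²/s².
- Low end: p = 0.10, d = 0.63, s = 4 gives 1 + 0.10 × 0.397/16 = 1.002
- Middle: p = 0.25, d = 1.26, s = 3 gives 1 + 0.25 × 1.588/9 = 1.044
- High end: p = 0.50, d = 1.26, s = 2 gives 1 + 0.50 × 1.588/4 = 1.198

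Over the grid p = 0.10, 0.25, 0.50; d = 0.63, 1.26; s = 2, 3, 4, 15 of the 18 combinations stay below 5%.

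**5. Bladder volume.** At 1 kg per litre, a difference of 0.2 L is 0.2 × 2.205 = 0.44 lb and 0.5 L is 1.10 lb. At a height of 1.70 m this is 0.2/2.89 = 0.07 to 0.5/2.89 = 0.17 kg/m² of BMI. Only the difference between visits enters the change.

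**The case against.** The strongest case on the other side has five parts.

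- **Existing steps already help.** Outerwear is removed before both waist and weight, which deals with much of any seasonal clothing effect. This stands; what remains is the shirt and other indoor clothing.
- **The no-void instruction is uniform.** It applies at every visit and in both arms, so it partly standardises bladder state. This stands too: bladder volume is mainly noise. A reader might infer that participants arrive with deliberately full bladders, or without having voided at all that day. The text does not support that; it asks only that they not void immediately before the visit.
- **Between-arm bias is unlikely.** Section 4.2 describes the pharmacist as blinded to diet group, so error should not differ by arm. This stands, and limits Aim 2 to a loss of precision that is usually small.
- **The 12% is a corner case.** At an SD of 4 cm it needs 40% of participants to move in one direction, none to move back, and 2 mm of cloth. This stands, and is why the range has to be quoted.
- **The gap may be filled elsewhere.** Section 4.3 credits an outside manual for its anthropometry, section 5.1 points to an Appendix G on measurement procedures, and the recording form itself is not shown. None can be checked here. Section 4.4 lists the form's contents without a field for shirt state, but the safe statement is that the supplied text does not require one.

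None of this supplies a rule that holds shirt state constant or places urine collection before the body measurements.

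**Conclusion.** The point holds as a cheap improvement to procedure, of low severity. Change in waist, weight or BMI and body composition can include differences in clothing and bladder volume between visits. It does not follow that it always does, nor that the diet comparison is biased. For Aim 2 the effect is mostly non-differential noise. For Aim 1 a small directional shift is possible.

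Under the assumed inputs, the waist artefact is 0.13 to 0.50 cm on average, and the false-positive rate of a pre-post test with n = 40 and SD 4 cm runs from 5.4%, barely above nominal, to 12%. The weight artefact for an individual is 0.4 to 1.1 lb for an assumed bladder difference of 0.2 to 0.5 L. How far bioimpedance readings respond to bladder urine cannot be judged from the documents.

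A reader might infer that the trial's main result is at risk. It is not: the primary lipid outcomes do not depend on any of these measurements.

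**What to change.** In section 4.3, with one matching field on the clinical data recording form in section 4.4:

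1. Measure waist on skin where the participant agrees, and otherwise over one thin layer. Limiting the layer matters, because repeating an over-the-shirt measurement still lets cloth thickness vary.
2. Record the state (skin or thin layer) at baseline and use the same state at weeks 6 and 12.
3. Weigh in one light indoor layer at every visit.
4. Collect the urine sample first at each visit, before weight, bioimpedance and waist.

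The cost is one tick-box and a fixed order for steps already performed, with no added visit or procedure. The downside is that a participant who declines skin measurement at baseline stays measured over a thin layer throughout.
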